7. ASSESSMENTS

Every effort should be made to ensure that the protocol required tests and procedures are completed as described. However it is anticipated that from time to time there may be circumstances, outside of the control of the investigator, that may make it unfeasible to perform the test. In these cases the investigator will take all steps necessary to ensure the safety and well-being of the patient. When a protocol required test cannot be performed the investigator will document the reason for this and any corrective and preventive actions which he/she has taken to ensure that normal processes are adhered to as soon as possible. The study team will be informed of these incidents in a timely fashion.

7.1. Safety Assessment

Safety assessments will include collection of AEs, SAEs, vital signs and physical examination, ECG (12-lead), laboratory assessments, including pregnancy tests and verification of concurrent medications.

7.1.1. Pregnancy Testing

MK-3475 may have adverse effects on a fetus *in utero*. Furthermore, it is not known if MK-3475 has transient adverse effects on the composition of sperm. See [Section 8.10](#) for exposure during pregnancy. The current MK-3475 IB contains a full description of non-clinical reproductive toxicology. In the case of PF-05082566, reproductive toxicology has not been characterized.

For female patients of childbearing potential, a serum or urine pregnancy test, with sensitivity of at least 25 mIU/mL, will be performed on two occasions prior to starting study therapy - once at the start of screening and once at the baseline visit, immediately before investigational product administration, and at the End of Treatment visit. Following a negative pregnancy result at screening, appropriate contraception must be commenced and a further negative pregnancy result will then be required at the baseline visit before the patient may receive the investigational product. Pregnancy tests will also be routinely repeated at every cycle during the active treatment period, at the end of study therapy and additionally whenever one menstrual cycle is missed or when potential pregnancy is otherwise suspected. In the case of a positive hCG test, the patient will be withdrawn from study medication but may remain in the study.

Additional pregnancy tests may also be undertaken if requested by IRB/Ethics Committee (EC) or if required by local regulations.

7.1.2. Adverse Events

Assessment of AEs will include the type, incidence, severity (graded by the National Cancer Institute Common Terminology Criteria for Adverse Events [NCI CTCAE] version 4.03) timing, seriousness, and relatedness.

AEs that occur during the study, including baseline signs and symptoms, will be recorded on the AEs CRF page.

7.1.2.1. MK-3475 Adverse Events of Special Interest

Selected non-serious and serious AEs are also known as Events of Clinical Interest (ECI) and must be recorded as such on the Adverse Event case report forms and reported within 24 hours to the Sponsor either by electronic media or paper.

ECIs for this trial include:

1. An overdose of Sponsor's product, as defined in [Section 8.4](#) - Medication Errors, that is not associated with clinical symptoms or abnormal laboratory results.
2. An elevated AST or ALT lab value that is greater than or equal to 3X the upper limit of normal and an elevated total bilirubin lab value that is greater than or equal to 2X the upper limit of normal and, at the same time, an alkaline phosphatase lab value that is less than 2X the upper limit of normal, as determined by way of protocol-specified laboratory testing or unscheduled laboratory testing.

Note: These criteria are based upon available regulatory guidance documents. The purpose of the criteria is to specify a threshold of abnormal hepatic tests that may require an additional evaluation for an underlying etiology. The trial site guidance for assessment and follow up of these criteria can be found in the Investigator Trial File Binder (or equivalent).

3. In the event a patient develops any of the following AEs, a detailed narrative of the event should be reported as an ECI to the Sponsor within 24 hours of the event:
 - a. Grade ≥ 3 diarrhea;
 - b. Grade ≥ 2 colitis;
 - c. Grade ≥ 2 pneumonitis;
 - d. Grade ≥ 3 hypo- or hyperthyroidism.

A separate guidance document has been provided entitled “Event of Clinical Interest and Immune-Related Adverse Event Guidance Document.” This document can be found in the administrative binder and provides guidance regarding identification, evaluation and management of ECIs and irAEs. Additional ECIs are identified in this guidance document and also need to be reported to the SPONSOR within 24 hours of the event.

Patients should be assessed for possible ECIs prior to each dose. Laboratory results should be evaluated and patients should be asked for signs and symptoms suggestive of an immune related event. Patients who develop an ECI thought to be immune-related should have additional testing to rule out other etiologic causes. If laboratory results or symptoms

indicate a possible immune-related ECI, then additional testing should be performed to rule out other etiologic causes. If no other cause is found, then it is assumed to be immune-related.

ECIs that occur to any patient from the date of first dose through 90 days following cessation of treatment, or the initiation of a new anticancer therapy, whichever is earlier, whether or not related to the Sponsor's product, must be reported within 24 hours to the Sponsor either by electronic media or paper. Sponsor Contact information can be found in the administrative binder.

7.1.3. Laboratory Safety Assessment

Hematology, blood chemistry, coagulation and urinalysis will be carried out at the time points described in the Schedule of activities (see the [Schedule Of Activities](#) and [Table 4](#)) and analyzed at local laboratories. Thyroid function assessments will include T3, FT4, and thyroid stimulating hormone (TSH). In the presence of clinical suspicion of hypopituitarism or hypoadrenalism, laboratory testing should include one or both of the following: adrenocorticotrophic hormone (ACTH) and cortisol levels before and 30-60 minutes after corticotrophin stimulation. Urinalysis will include measurement of pH, specific gravity, protein/albumin, glucose, blood/hemoglobin, ketones/acetone. Urine dipstick for urine protein: if positive collect 24-hr and microscopic (Reflex Testing). Urine dipstick for urine blood: if positive collect a microscopic (Reflex Testing).

7.1.4. Vital Signs and Physical Examination

Patients will have a physical exam that will include major body systems, weight, blood pressure, heart rate, assessment of ECOG status and height; height will be measured at baseline only. Physical exams will be performed at the time points described in the [Schedule Of Activities](#).

7.1.5. ECG Assessments

Electrocardiogram (ECG): Triplicate 12-lead (with a 10-second rhythm strip) tracing in the supine or semi-recumbent position will be used for all ECGs. It is preferable that the machine used has a capacity to calculate the standard intervals automatically. At each time point, three consecutive 12 lead ECGs will be performed approximately 2 minutes apart to determine mean QTc. When coinciding with blood sample draws for PK, ECG assessment should be performed prior to blood sample collection, such that the blood sample is collected at the nominal time. If the mean QTc interval is prolonged (>500 msec), then the ECGs should be re-evaluated by a qualified person at the center for confirmation. Clinically significant abnormal findings in baseline ECGs will be recorded as medical history. Clinically significant findings seen on the follow-up ECGs should be recorded as adverse events. ECG assessments beyond Screening will not be required for patients in dose expansion cohorts (see the [Schedule Of Activities](#)). Additional ECGs may be performed as clinically indicated. While pre-dose ECG assessments will be required for all patients, post-dose ECG assessments will be required only for patients in dose escalation cohorts.

Prior to concluding that an episode of prolongation of the QTcF interval is due to study drug, thorough consideration should be given to potential precipitating factors (eg, change in patient clinical condition, effect of concurrent medication, electrolyte disturbance) and possible evaluation by specialist.

If patient experiences a cardiac or neurologic AE (specifically syncope, dizziness, seizures, or stroke), an ECG (triplicate) should be obtained at the time of the event.

When matched with PK sampling, the ECG must be carried out before each PK sample drawing such that the PK sample is collected at the nominal time (ie, the timing of the PK collections over rides the timing of the ECG collections).

7.2. Pharmacokinetics Assessments (Dose Escalation and Dose Expansion Cohorts)

PK samples will be assayed for PF-05082566, and MK-3475 using a validated analytical method in compliance with Pfizer (PF-05082566) or Merck (MK-3475) standard operating procedures. Details regarding the collection, processing, storage and shipping of the blood samples will be provided in the study manual.

CCI

All efforts will be made to obtain the pharmacokinetic samples at the scheduled nominal time relative to dosing. However, samples obtained within 10% of the nominal time (eg, within 6 minutes of a 60 minute sample) will be considered protocol compliant, and the exact time of the sample collection noted on the CRF. If a scheduled blood sample collection cannot be completed for any reason, the missed sample time may be re-scheduled with agreement of clinical investigators, patient and Sponsor.

In addition to samples collected at the scheduled times, an additional blood sample should be collected from patients experiencing unexpected and/or serious AE's and the date and time documented in the CRF.

As part of understanding the pharmacokinetics of the study drug, samples may be used for evaluation of the bioanalytical method. This additional characterization will be used for internal exploratory purposes and will not be included in the clinical report. Samples collected for this purpose will be retained in accordance to local regulations and if not used within this timeframe, will be destroyed.

7.2.1. PF-05082566

Blood samples will be collected for PK of PF-05082566 at the following time points:

- During Cycle 1-4 on (a) Day 1 at pre-dose and end of infusion;
- During Cycle 5 on (b) Day 1 at pre-dose, end of infusion, and at 2, 6 and 24 hr post start of infusion; (c) on Days 8 (192 hours) and 15 (360 hours) after start of infusion (See [Section 7.2](#) above for guidelines on timing of blood draws);

- During Cycle 6 on (d) Day 1 at pre-dose only;
- During Cycle 7 on (e) Day 1 at pre-dose, end of infusion, 24 hrs post start of infusion and on Day 8.

Beyond Cycle 7, PK samples will be collected at pre-dose, every two cycles up to Cycle 12, every 4 cycles thereafter, and at the End of Treatment visit.

For patients in expansion cohorts: The same PK schedule will be followed for at least 10 patients in total from all expansion cohorts. For other patients (in all expansion cohorts), predose samples on Day 1 will be collected for Cycles 1, 3, 5, 6 and 7. Beyond Cycle 7, PK samples will be collected at pre dose (Day 1), for every 2 cycles up to Cycle 12, and every 4 cycles thereafter. Timing of sampling may be modified based on emerging PK data. For patients discontinuing from the study, a PK sample should be collected at the End of Treatment assessment day.

7.2.2. MK-3475

Blood samples will be collected for PK of MK-3475 at the following time points:

- During Cycle 1- 4 on (a) Day 1 at pre-dose and end of infusion;
- During Cycle 5 on (b) Day 1 at pre-dose and end of infusion;
- During Cycle 7 on (c) Day 1 at pre-dose, end of infusion, 24 hrs, and on Day 8 (192 hours) post start of infusion (See [Section 7.2](#) for guidelines on timing of blood draws).

Beyond Cycle 7, PK samples will be collected at pre-dose, every two cycles up to Cycle 12, and every 4 cycles thereafter. Additionally, PK samples will be collected at 28 days after end of MK-3475 treatment (during the End of Treatment visit) and during follow-up at 3 months and 6 months after the end of MK-3475 treatment.

For patients in expansion cohorts: The same PK schedule will be followed for at least 10 patients in total from all expansion cohorts. For other patients (in all expansion cohorts), predose samples on Day 1 will be collected for Cycles 1, 3, 5 and 7. Beyond Cycle 7, PK samples will be collected at pre dose (Day 1), for every 2 cycles up to Cycle 12, and every 4 cycles thereafter. Additionally, PK samples will be collected at 28 days after end of MK-3475 treatment (during the End of Treatment visit) and during follow-up at 3 months and 6 months after the end of MK-3475 treatment.

For patients ending from the study, PK samples should be collected at the End of Treatment assessment day. PK sampling schedule may be modified based on emerging PK data.

CCI

[REDACTED]

[REDACTED]

[REDACTED]

[REDACTED]

[REDACTED]

I [REDACTED]

I [REDACTED]

[REDACTED]

[REDACTED]

[REDACTED]

CCI

[REDACTED]

[REDACTED]

I [REDACTED]

I [REDACTED]

[REDACTED]

[REDACTED]

7.4. Banked Biospecimen (Blood)

7.4.1. Markers of Drug Response

Studying the variation in genetic markers and other biomarkers may help to explain some of the variability in response seen with some drugs among different individuals. This is referred to as pharmacogenomic/biomarker research. Comparing the deoxyribonucleic acid (DNA), ribonucleic (RNA), protein, and metabolite variation patterns of patients who respond well and those who respond poorly to treatment may help to better define the most appropriate group of patients in which to target a given treatment. Collecting biospecimens for exploratory pharmacogenomic/biomarker analyses and retaining them in the Pfizer BioBank makes it possible to better understand the drug's mechanism of action and to seek explanations for differences in, for example, exposure, efficacy, tolerability, or safety not anticipated prior to the beginning of the study. Providing these biospecimens is a required study activity for study sites and patients, unless prohibited as such by local regulations or ethics committee decision.

To protect patients' confidentiality, the banked biospecimens and data generated from them will be coded with the patient's study identification (ID) number. Samples will be kept in a facility accessible only by badge-swipe. Data will be stored on password-protected computer systems. The key between the code and the patient's personal identifiers will be held at the study site; the researchers using the biospecimens and data generated from them will not have access to the key nor any personally identifying information. Biospecimens will only be used for the purposes described here and in the informed consent document/patient information sheet; any other uses require additional ethical approval. Unless a time limitation is required by local regulations or ethical requirements, biospecimens will be stored indefinitely to allow for future research on the topics described here, including research conducted during the lengthy drug development process and also postmarketing research. Patients can withdraw their consent for the use of their biospecimens at any time by making a request to the investigator, in which case any remaining biospecimen will be destroyed; data already generated from the biospecimens will continue to be stored to protect the integrity of existing analyses. It is very unlikely that results generated from the biospecimens will have any clinical, diagnostic, or therapeutic implications for the individual study participants. Patients are notified in the informed consent document/patient information sheet that their results will not be given to them, unless required by local laws or regulations, in which case results will be returned via the investigator. Results will not be provided to family members or other physicians, nor will they be recorded in the patient's medical record. There is no intention to contact patients after completion of the clinical study.

A 4-mL blood biospecimen, Prep D1 (K₂ edetic acid (ethylenediaminetetraacetic acid)(EDTA)) whole blood collection optimized for DNA analysis), will be collected on Day 1 of Cycle 1 (pre-dose) to be retained for potential pharmacogenomic/biomarker analyses related to drug response, unless prohibited by local regulations or ethics committee decision. For example, putative safety biomarkers, drug-metabolizing enzyme genes, drug-transport protein genes, or genes thought to be related to the mechanism of drug action may be examined.

Detailed collection, processing, storage, and shipment instructions are provided in the central laboratory manual.

It is possible that the use of these biospecimens may result in commercially viable products. Patients will be advised in the informed consent document/patient information sheet that they will not be compensated in this event.

7.4.2. Additional Research

Unless prohibited by local regulations or ethics committee decision, patients will be asked to indicate on the consent form whether they will allow the banked biospecimens to also be used for the following research:

- Investigations of the disease under study in the clinical study, and related conditions;
- Biospecimens may be used as controls. This includes use in case-control studies of diseases for which Pfizer is researching drug therapies; use in characterizing the natural variation amongst people in genes, RNA, proteins, and metabolites; and use in developing new technologies related to pharmacogenomics/biomarkers.

Patients need not provide additional biospecimens for the uses described in this section; the biospecimens specified in the [Markers of Drug Response](#) Section will be used. Patients may still participate in the clinical study if they elect not to allow their banked biospecimens to be used for the additional purposes described in this section.

7.5. Immunogenicity Assessments (ADA)

ADA (anti-drug antibodies) blood samples will be assayed for anti-PF-05082566, and anti-MK-3475 antibodies using a validated analytical method in compliance with Pfizer (anti-PF-05082566) or Merck (anti-MK-3475) standard operating procedures. All the samples that are positive for ADA may also undergo characterization for neutralizing antibodies.

As part of understanding the pharmacokinetics of the study drug, samples may be used for evaluation of the bioanalytical method. This additional characterization will be used for internal exploratory purposes and will not be included in the clinical report. Samples collected for this purpose will be retained in accordance to local regulations and if not used within this timeframe, will be destroyed.

Blood samples (2 mL for PF-0508 2566 and 6 ml for MK-3475) for evaluation of immunogenicity of PF-05082566/MK-3475 will be collected at the following time points:

7.5.1. Immunogenicity to PF-05082566

- In Cycle 1, 3,5, 7 Day 1 at pre-dose;
- Cycles >7, Day 1 at predose for every two cycles up to Cycle 12, and every 4 cycles thereafter.

For patients discontinuing study drug treatment, immunogenicity samples should be collected at the End of Treatment assessment day. If ADAs are detected, additional samples may be collected approximately every 3 months (coinciding with disease assessment visits) until ADA levels return to baseline. Samples will be analyzed by a laboratory to be identified by Pfizer. See the Laboratory Manual for additional details.

7.5.2. Immunogenicity to MK-3475

- Cycle 1, 3, 5, and 7 Day 1 at pre-dose;
- Cycles >7, Day 1 at predose for every two cycles up to Cycle 12, and every 4 cycles thereafter;
- Additionally, ADA samples will be collected at 28 days, and during Follow-up (3 months and 6 months after end of MK-3475 treatment).

For patients ending from the study, immunogenicity samples should be collected at the End of Treatment assessment. MK-375 samples will be analyzed by a laboratory to be identified by Merck. See the Laboratory Manual for additional details.

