22. **Blood for PF-05082566 Pharmacokinetics:** Blood samples will be collected during Cycle 1-4 on (a) Day 1 at pre-dose and end of infusion; (b) During Cycle 5 on Day 1 at pre-dose, end of infusion, and at 2, 6, and 24 hrs after the start of infusion; (c) on Days 8 (192 hours), and 15 (360 hours) after start of infusion (See [Section 7.2](#) for guidelines on timing of blood draws); (d) During Cycle 6 on Day 1 at pre-dose; (e) During Cycle 7 on Day 1 at pre-dose, end of infusion, 24 hrs after the start of infusion and on Day 8; and (f) Beyond Cycle 7, PK samples will be collected at pre-dose, for every 2 cycles up to Cycle 12, every 4 cycles thereafter, and at the End of Treatment visit. **For patients in expansion cohorts**, same PK schedule will be followed for at least 10 patients in total from all expansion cohorts. For other patients (all expansion cohorts), predose samples on Day 1 will be collected for Cycles 1, 3, 5, 6 ([Section 7.2.1](#)) and 7. Beyond Cycle 7, PK samples will be collected at pre-dose, for every 2 cycles up to Cycle 12, and every 4 cycles thereafter. Timing of sampling may be modified based on emerging PK data. For patients discontinuing from the study, a PK sample should be collected at the End of Treatment assessment.
23. **Blood for MK-3475 Pharmacokinetics:** Blood samples will be collected (a) During Cycle 1- 4 on Day 1 at pre-dose and end of infusion; (b) During Cycle 5 on Day 1 at pre-dose; and end of infusion; (c) During Cycle 7 on Day 1 at pre-dose, end of infusion, 24 hrs, and on Day 8 (192 hrs) after start of infusion (See [Section 7.2](#) for guidelines on timing of blood draws). Beyond Cycle 7, PK samples will be collected at pre-dose every two cycles up to cycle 12, and every 4 cycles thereafter. Additionally, PK samples will be collected at 28 days, 3 months, and 6 months after the end of MK-3475 treatment. **For patients in an expansion cohort**, the same PK schedule will be followed for at least 10 patients in total from all expansion cohorts. For other patients (all expansion cohorts), predose samples on Day 1 will be collected for Cycles 1, 3, 5 and 7. Beyond Cycle 7, PK samples will be collected at pre-dose (Day 1), every 2 cycles up to Cycle 12, and every 4 cycles thereafter. Timing of sampling may be modified based on emerging PK data. For patients withdrawing from the study, a PK sample should be collected at the End of Treatment assessment.
24. **CCI**

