32. **Follow Up:** Patients should be evaluated up to 90 days after last dose of study treatment. Refer to the protocol for specific guidelines. Patients continuing to experience toxicity following discontinuation of study treatment will continue to be followed at least every 4 weeks until resolution or determination, in the clinical judgment of the Investigator, that no further improvement is expected. PK and immunogenicity samples should be collected as described in the PK and Immunogenicity Assessment section in Schedule of Activities ([Table 3](#)). Patients whose disease has not progressed at the end of treatment will enter into disease follow-up. During this follow-up period, patients will have disease assessments performed every 12 weeks \pm 7-days. Once patients have exhibited disease progression or began a new anti-cancer therapy, or 6-month follow-up from the date of the first dose of the last enrolled patient, whichever occurs first, they will be withdrawn from the study. See [Section 4.3.1](#) Contraception for guidelines on contraception checks during this period.
33. **De novo tumor biopsy for biomarker assessment (Dose escalation):** For patients in dose-escalation cohorts, unscheduled optional de novo tumor biopsies may be collected at the discretion of the investigator and sponsor to support the assessment of disease progression.
34. **De novo tumor biopsy for biomarker assessment (Expansion cohorts):** Mandatory for patients in expansion cohorts only. A de novo biopsy will be required at study entry followed by a second biopsy at the time of the Week 9 scans (after 3 cycles of treatment).
35. **Continued Treatment Beyond Cycle 8:** This will be on a reduced visit schedule (Day 1 of each cycle), or as clinically indicated.
36. **Thyroid Function Tests:** To be collected every 2 cycles for the first 8 cycles, and then every 4 cycles (Cycles 1, 3, 5, 7, 11, 15 etc.).
37. **Hepatitis B and C Tests:** Conduct tests for hepatitis B surface antigen, core antibody, and anti-hepatitis C. Other tests may be conducted per standard practice to confirm an active hepatitis infection.

Table 4. Required Laboratory Tests

SAFETY LABORATORY REQUIREMENTS	
Refer to the Schedule of Activities table for specific timepoints and instructions	
Assessments	
Hematology Panel:	Chemistry Panel:
Absolute Neutrophil Count	Sodium
Hemoglobin	Potassium
	Total Calcium
Platelet Count	Creatinine
WBC with differential (5-part if available)	Albumin

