6.2. Study Period

For treatment period procedures, see the [Schedule Of Activities](#) and [ASSESSMENTS](#) sections. The End of Treatment assessments are to be performed approximately 28 days after the last dose of study drug. Obtain these assessments if not completed during the previous week on study (during the previous 6 weeks on study for tumor assessments).

Patients whose disease has not progressed at the end of treatment will enter into disease follow-up. During this follow-up period, patients will have disease assessments performed every 12 weeks \pm 7-days. Once patients have exhibited disease progression or began a new anti-cancer therapy (not including radiotherapy to a non-target tumor), whichever occurs first, the date of progression will be recorded on the appropriate CRF page and they will be withdrawn from the study. No further data will be collected from these patients. Patients continuing to experience treatment-related toxicity following discontinuation of study treatment will continue to be followed at least every 4 weeks until resolution or determination, in the clinical judgment of the Investigator, that no further improvement is expected.

For follow-up procedures see [Schedule Of Activities](#).

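### The 6-month post-treatment MK-3475 PK and ADA samples cannot be reconciled with the withdrawal rules, and the 3-month samples are left in contradiction, so late ADA may be seen only in an outcome-selected subset

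*Protocol*

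**What the plan says.** **Sampling requirement.** For ADA, Protocol Section 7.5.2 states: "Additionally, ADA samples will be collected at 28 days, and during Follow-up (3 months and 6 months after end of MK-3475 treatment"). For PK, Section 7.2.2 asks for samples at the 28-day End of Treatment visit and "during follow-up at 3 months and 6 months after the end of MK-3475 treatment", and repeats this for the expansion cohorts. Schedule of Activities footnotes 23 and 30 agree, and Table 3 marks both samples in its Follow-up column. None of these places limits the samples to patients without progression.

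**Withdrawal rules.** Section 6.2 and footnote 32 admit to disease follow-up only patients who have not progressed when treatment ends. Footnote 32 then names three triggers. The first two are progression and new anticancer therapy. The third is a calendar limit, worded as follows: "or 6-month follow-up from the date of the first dose of the last enrolled patient, whichever occurs first, they will be withdrawn from the study". Section 6.2 names the first two only and concludes: "they will be withdrawn from the study. No further data will be collected from these patients". Its next sentence keeps unresolved treatment-related toxicity under follow-up. It contains no such sentence for PK or ADA.

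**Text pointing the other way.** Footnote 32 opens with "Patients should be evaluated up to 90 days after last dose of study treatment" and directs that PK and immunogenicity samples follow Table 3. Protocol Section 6.3 gives a non-exhaustive list of reasons for leaving study follow-up, and neither progression nor new therapy is on it.

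**The concern.** A site cannot follow the literal wording of both Section 6.2 and Section 7.5.2 for a patient who stops treatment because of progression. If sites follow the withdrawal wording, the late samples come only from patients who stopped without progression, have since stayed free of progression and new therapy, and reach the sampling date before the calendar trigger. Whether a late sample exists then depends on outcome.

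This matters because immunogenicity in combination is a secondary objective. SAP Section 6.2.6 plans ADA positivity at any time in the study, time of onset, duration, and the impact of ADA on PK, safety and efficacy, as data permit. SAP Section 4.3.4 admits any patient with one sample for either drug. SAP Section 5.3.1 evaluates data as observed, without imputation. SAP Section 6.2.6 sets no denominator for patients who have a given post-treatment sample. Under the strict reading, patients doing well would have up to two more chances to test positive than patients who progressed. An association between ADA and efficacy could arise from that alone.

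**Working it through.** The plan states no figure that this point disputes. The check compares the sampling times with the withdrawal rules.

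**Inputs.** MK-3475 half-life 21 days (Protocol Section 1.2.9.1.1). One month = 30.4375 days (SAP Section 5.2.8). Sampling at 28 days, 3 months and 6 months after treatment. Planned maximum of 32 cycles of 21 days (Protocol Section 5.3.3).

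**1. Evaluation window.** 3 months = 3 × 30.4375 = 91.3 days, and 6 months = 182.6 days. The 90-day evaluation in footnote 32 roughly covers the first and falls about 93 days short of the second.

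**2. Drug remaining at each sample.** With simple exponential decay, the fraction left is 0.5^(t/21):

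| Sample | Days | Half-lives | Fraction left |
|---|---|---|---|
| Day 28 | 28 | 1.33 | 39.7% |
| 3 months | 91.3 | 4.35 | 4.9% |
| 6 months | 182.6 | 8.70 | 0.24% |

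The samples in doubt are the only scheduled post-treatment ones taken when little drug is left. How far that improves ADA detection depends on the assay's drug tolerance, which the documents do not give.

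**3. Calendar trigger (footnote 32 only).** Let F be the last enrolled patient's first-dose date and D a given patient's last dose. The trigger falls at F + 6 months.

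- 6-month sample: D + 6 ≤ F + 6, so D ≤ F.
- 3-month sample: D + 3 ≤ F + 6, so D ≤ F + 3 months.

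For a patient who starts L months before F and is dosed over T months, D = F − L + T. The 6-month sample then needs L ≥ T, and the 3-month sample needs L ≥ T − 3.

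| T (months) | L needed, 6-month sample | L needed, 3-month sample |
|---|---|---|
| 6 | 6 | 3 |
| 12 | 12 | 9 |
| 31 × 21 / 30.4375 = 21.4 | 21.4 | 18.4 |

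Anyone dosed after F misses the 6-month sample. The last enrolled patient (L = 0) misses it after a second dose. This step needs no assumption about progression.

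**4. Progression and new therapy.** A patient who progresses at or before the end of treatment does not enter disease follow-up and is withdrawn. Under Section 6.2 no later data are collected, so neither late sample is drawn. A patient who starts new therapy before month 3 or month 6 loses whatever sample is still outstanding.

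**5. Illustration of size (assumptions, not figures from the documents).** Suppose 10–40% of patients end treatment without progression, and the median time from then to progression or new therapy is 3–12 months. Under the strict reading, the share reaching a sample at month t is (share without progression) × 0.5^(t/median). The counts use the dose-escalation maximum of 45.

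- 6 months: from 0.10 × 0.5^(6/3) = 2.5% to 0.40 × 0.5^(6/12) = 28%, about 1 to 13 of 45.
- 3 months: from 0.10 × 0.5^(3/3) = 5% to 0.40 × 0.5^(3/12) = 34%, about 2 to 15 of 45.

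Calendar losses would come on top. The width of the range shows that the documents do not fix the size.

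**The case against.** The strongest reply is that withdrawal in Section 6.2 was meant to end disease follow-up and nothing else. An absolute bar on further data would contradict the toxicity follow-up in the very next sentence, the 90-day SAE reporting period in Section 8.2, and the rule there that deaths in that period are reported whatever treatment intervenes. Footnote 32 evaluates patients to 90 days and sends PK and ADA sampling to Table 3 without regard to progression. Section 6.3 does not list progression as a reason to leave follow-up. The calendar trigger stands in one clause of one footnote, while SAP Section 2 sets its cut-off 24 months after the last patient's first dose.

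Much of this stands for the 3-month sample, where the passages conflict and do not clearly exclude anyone. It does not rescue the 6-month sample, which lies beyond the 90-day evaluation as well as outside the withdrawal rules. Nor does any sentence say which instruction governs: Section 6.2 makes an exception for toxicity and is silent on PK and ADA.

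A reader might also infer that overall ADA incidence, the drug-interaction check and MK-3475 PK all rest on an unrepresentative few. The documents do not support that:

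- ADA is sampled before dosing at Cycles 1, 3, 5 and 7 and periodically afterwards, and again at the 28-day End of Treatment visit, whatever the later outcome.
- The interaction check in Protocol Sections 3.1 and 9.5.1.1 uses steady-state PK and ADA formation.
- Section 9.5.1.1 takes MK-3475 PK parameters from a population model, which does not depend on these draws alone.
- No discontinuation or progression rates are given, so the sampled group cannot be called small as a matter of fact.
- The late draws concern MK-3475 only. PF-05082566 ADA has its own rule in Section 7.5.1.

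**Conclusion.** The conflict is real and is one of wording. It is firm for the 6-month MK-3475 PK and ADA samples: under the rules as written they cannot be obtained from patients who have progressed or started new therapy, or, under footnote 32, from anyone dosed after the last enrolled patient's first dose. For the 3-month samples the protocol contradicts itself.

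On the strict reading, the damage is confined to late post-treatment ADA: late onset, persistence and the any-time positivity count. These would be observed in an outcome-selected subset, which can bias the planned comparison of ADA with efficacy and safety. On-treatment and Day 28 ADA, the steady-state interaction check and the population PK analysis are largely unaffected. The size of the loss cannot be derived from the documents. The 1 to 13 of 45 above rests wholly on assumed rates, and the residual-drug percentages rest on the 21-day half-life and simple exponential decay.

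**What to change.** **Protocol Section 6.2 and footnote 32.** Use the same text in both places, for example:

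> Disease progression, new anticancer therapy or the calendar cut-off ends disease assessments only. The scheduled 3- and 6-month MK-3475 PK and ADA samples are still drawn unless the patient withdraws consent. The start date of any new anticancer therapy is recorded.

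Leave the 90-day evaluation window unchanged, because it matches the 90-day SAE and event-of-clinical-interest reporting periods. Extending it would create a new mismatch.

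**SAP Section 6.2.6.** Report the number of patients sampled at 28 days, 3 months and 6 months after treatment. Use that number as the denominator for post-treatment ADA at each time, and describe the patients not sampled.

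**Alternative.** If patients will not be kept for these visits, delete the 3- and 6-month draws from Sections 7.2.2 and 7.5.2, footnotes 23 and 30 and Table 3. State that MK-3475 ADA status is known only to 28 days after the last dose.

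**Cost.** Amendment wording. The draws are already scheduled, so no procedure is added. Some patients who have progressed will decline, and study close may be somewhat later.
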